Primary outcome: investigate the immediate postural response of the pelvis, lumbar and dorsal spine in search of balance during the passive elevation of 3 cm and 7 cm of the heels with a non-invasive tool in non-users of high-heeled shoes.

Secondary outcome: investigate if there is a different response in the two sexes. Assuming that the reaction to heels can also be linked to the habit of wearing high-heeled shoes, use the response of a group of males, who are assumed to have never worn high-heeled shoes (7 cm) in their own life, can further clarify what type of response occurs in the search for immediate postural balance of the pelvis and the dorsal-lumbar spine after the raising of the heels.

Study design

Cross sectional study. Monocentric.

Duration of the study

Six months

Materials and methods

Setting: OSCE (Osteopathic Spine Center Education), osteopathic school based in Bologna.

Population: 100 students (50 females and 50 males) to be enrolled in OSCE school by making announcements during the lessons. The number of subjects to be evaluated was decided on the basis of the most recent work which used the same methodology, which evaluated a sample of 36 women (Schroeder and Hollander 2018). A similar number between males and females was set to improve the statistical comparison.

Following the ethical principles of the Declaration of Helsinki, a paper information will be provided where there will be an explanation of the intent and purpose of the study to all subjects prior to their participation; in addition, a paper consent will be provided, together with the information, on which to obtain the voluntary written informed consent.

Inclusion criteria: asymptomatic young subjects.

Exclusion criteria:

- structural or neurological anomalies that may prevent from maintaining an upright position for 5 sec. with their heels elevated on a 7 cm high basement;
- habitual users of shoes with 7 cm high heels, with a frequency of at least twice a week and / or less than 3 hours / week as proposed by a previous study (de Oliveira Pezzan et al. 2011);

- low back pain in the past 30 days.

Measurement method

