A three-dimensional posterior surface analysis is performed with the Formetric 4D® rasterstereographic device (Diers International GmbH, Schlangenbad, Germany). The device, already supplied at the Spine Center rehabilitation center in Bologna and made available free of charge for the study, is non-invasive and non-dangerous. The analysis of the spine curve with rasterstereography is performed with a purely optical modality.

[figure not shown]

fig. 1 - Scheme of the spinometric parameters to be recorded: pelvic inclination, lordotic angle, kyphotic angle.

[figure not shown]

fig. 2 - Scheme of the spinometric parameters to be recorded: cervical and dorsal arrow, anterior flexion of the trunk.

Investigated parameters

The data collected by the Formetric evaluation will be:

- 1) pelvic tilt angle (PI), the angle determined by the vertical and the tangent to lumbosacral junction (ILS);
- 2) ITL-ILS lordotic angle, measured between the tangents of the thoracolumbar junction (ITL) and the lumbosacral junction (ILS);
- 3) ICT-ITL kyphotic angle, measured between the tangents of the cervicothoracic junction (ICT) and the thoracolumbar junction (ITL); see fig. 1;
- 4) lumbar arrow (FL) horizontal distance in millimeters from the vertical line that passes through the kyphotic apex in the lumbar spine;
- 5) cervical arrow (FC) (horizontal distance in millimeters from the virtual vertical plumb line that passes through the kyphotic apex in the cervical spine);
- 6) antero-posterior flexion of the trunk (Trunk Inclination-TI) measured as the angle between the vertical line and the line passing through the prominent cervical vertebra (VP) to the line connecting the two dimples (DM); see fig. 2.

Participants will provide information on age, height and weight. A questionnaire will be administered to standardize the types of high-heeled shoes used and to verify their frequency of use.

Evaluation Protocol

- 1) sample 1: barefoot neutral position;
- 2) sample 2: barefoot neutral position;
- 3) sample 3: 3 cm rise under both heels;
- 4) sample 4: 7 cm rise under both heels.

The positioning with respect to the measurement system will be carried out according to the indications provided by the supplier.

To standardize the position subjects will be prepared for analysis as follows:

1. standing, back to the detection system, in a relaxed posture with the knees fully extended with bare feet on the floor (neutral position);

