2. bare trunk with pants and briefs lowered to half of the glutei
3. in the case of long hair, it will be required to tie it with suitable means (cap, hair clips, hair bands, etc.) so that the neck is visible up to the hairline;
4. rings, watches and necklaces will be removed to avoid any interference with light lines (necklaces in particular increase this probability).

In the third survey, the heel will be raised by inserting a plastic bar symmetrically under both heels, as proposed in previous studies in which wood was used (Bendix et 1984; Franklin et al. 1995), by 3 cm; for the fourth evaluation it will be 7 cm.

After the first evaluation in the neutral position, before the evaluation with the heel lift, a second evaluation will be performed under the same conditions to evaluate the reproducibility of the data. The time between the two assessments will be less than 1 minute and the subject will not change position.

The spinometric analysis will be performed by specialized operators; the data will be entered after anonymization with an identification code on an Excel spreadsheet; the statistical analysis will be performed with the Prisma statistical program.

Statistic analysis

Descriptive analysis will be performed to determine mean values and standard deviations (SD).

It will be used:

- Kolmogorov-Smirnov test to verify the normal distribution;
- intra-class correlation coefficient test (ICC) and the t-test for paired data to evaluate the repeatability of the data between the first and second detection in neutral conditions;
- One-way ANOVA and paired t-test for data for comparison between neutral position, heels raised by 3 cm and 7 cm in both males and females;
- Cohen's d will be calculated for the difference between neutral conditions (NEU) and those with the rise (3-7cm) (d = 0.20 indicates a small effect size, d = 0.50 an effect size mean and d = 0.80 a large effect).
- t-test for independent data to evaluate if there are significant differences between the different positions (0-3 cm-7cm) between males and females.

Statistical significance will be accepted for p values <0.05.

Data analysis will be performed using Prism 8 software (Graphpad Software, S. Diego).

Bibliography

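### The plan asks whether the sexes respond differently to heel lift, but does not clearly specify a test of a sex difference in change from neutral

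*Combined protocol and SAP*

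**What the plan says.** Under Primary outcome the protocol sets out to "investigate the immediate postural response of the pelvis, lumbar and dorsal spine in search of balance during the passive elevation of 3 cm and 7" (the last figure is also in centimetres), so a response is what happens to posture when the heels go up. The next item reads "Secondary outcome: investigate if there is a different response in the two sexes". The target of the secondary question is therefore a male-female difference in change from neutral.

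The Statistic analysis section has three items that bear on this:

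- The only between-sex analysis: "t-test for independent data to evaluate if there are significant differences between the different positions (0-3 cm-7cm) between males and females". It does not say whether the variable is the value at each height or the change from neutral.
- "One-way ANOVA and paired t-test for data for comparison between neutral position, heels raised by 3 cm and 7 cm in both males and females". The ANOVA is one-way, so it has no sex-by-position term.
- "Cohen's d will be calculated for the difference between neutral conditions (NEU) and those with the rise (3-7cm". This uses the difference from neutral but does not contrast the sexes.

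The Evaluation Protocol takes two neutral recordings; the second is listed as "sample 2: barefoot neutral position" and serves to check reproducibility. The plan does not say which of the two is the neutral reference.

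**The concern.** If the independent t-test is run on values at 0, 3 and 7 cm, it asks whether men and women have different spinal angles at a given height. The secondary outcome asks something else: whether they react differently to the lift. The two questions can have opposite answers.

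- A sex difference already present in neutral stance carries through to 3 and 7 cm and can be reported as a different response when there is none.
- A real difference in response can be missed, or hidden by a neutral difference of opposite sign.

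The within-sex analyses do not fill the gap. A significant change in one sex and a non-significant change in the other is not a test that the two changes differ.

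**Working it through.** The plan gives no power, effect size or SD for this comparison, so it has no figure to reproduce. The finding rests on the text; the figures below show only the consequence.

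**Inputs from the documents.** 50 females and 50 males (Population); significance at p < 0.05 (Statistic analysis).

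**Assumptions.** Two-sided testing; normal data; equal SDs; a neutral sex difference of 0 to 0.8 between-subject SD; a correlation r between positions of 0.3 to 0.95, equal for all pairs. All figures are per parameter.

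**1. Level test at 7 cm, identical response in both sexes.** The male-female difference at 7 cm then equals the neutral difference d (in SD). The noncentrality is d / √(2/50) = 5d, with 98 df and critical t = 1.984.

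| Neutral difference d | 5d | Level test significant |
|---|---|---|
| 0 | 0 | 5% |
| 0.2 | 1.0 | 17% |
| 0.3 | 1.5 | 32% |
| 0.5 | 2.5 | 70% |
| 0.8 | 4.0 | 98% |

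The change-score test removes d, so each test stays at 5%. If 3 cm and 7 cm changes are both tested without correction, at least one rejects in about 9%. A single 2-df sex-by-position test stays at 5%.

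**2. The same case, but the reader also uses the 0 cm result.** The misleading pattern is now 3 or 7 cm significant and 0 cm not (simulation, 40,000 runs per cell).

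| d | r = 0.5 | r = 0.8 | r = 0.9 |
|---|---|---|---|
| 0 | 7.5% | 5% | 3% |
| 0.2 | 17% | 10% | 7% |
| 0.3 | 24% | 14% | 10% |
| 0.5 | 20% | 13% | 9% |
| 0.8 | 2% | 2% | 1% |

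**3. A true response difference of 0.3 SD at 7 cm, equal neutral values.** The level test has 32% power. The SD of change is √(2(1 − r)), so the standardised effect is 0.3 / √(2(1 − r)).

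| r | Effect in SD of change | Change-test power |
|---|---|---|
| 0.3 | 0.254 | 24% |
| 0.5 | 0.300 | 32% |
| 0.7 | 0.387 | 48% |
| 0.8 | 0.474 | 65% |
| 0.9 | 0.671 | 91% |
| 0.95 | 0.949 | 99.7% |

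The change test gains power only above r = 0.5.

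**4. Cancellation.** Take a neutral difference of −0.3 SD and a response difference of +0.3 SD. The expected difference at 7 cm is −0.3 + 0.3 = 0, so the level test rejects in 5% at any r. The change test rejects in 32%, 65% and 91% at r = 0.5, 0.8 and 0.9.

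**The case against.** The document is a translation, and the sentence can be read as comparing between-position differences (0 to 3, 0 to 7) across the sexes. That would be the right contrast, and 0 cm would have to be named as its reference. This reading is possible, so the plan is not shown to have chosen a wrong test. But the sentence does not fix which test is run, and two analysts could follow it and answer different questions.

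On size, the 17% to 98% figures assume a reader who ignores the 0 cm comparison, although the level reading itself plans one. That is fair, and the second table is the better guide. Part of each rate there is ordinary chance, as the row for d = 0 shows. At r = 0.9 the 7% to 10% for differences of 0.2 to 0.5 SD is close to the 9% from two uncorrected change tests, so an uncorrected pair would gain little on that measure. At r = 0.5 and 0.8 the pattern is more frequent (10% to 24%), and the 2-df interaction test holds 5% throughout.

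The within-sex results and Cohen's d would also help a careful reader separate a change from a neutral offset, but they do not test the difference. Nothing in the documents suggests exact cancellation; it is an illustration. The choice of neutral reference also affects the primary comparison and adds no weight to this point.

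**Conclusion.** The concern holds and should be fixed. The stated secondary question is a sex difference in response; the only between-sex test is ambiguous and most naturally compares levels; and no other planned analysis supplies the contrast.

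The practical size is moderate and conditional. It depends on an assumed neutral sex difference and correlation between positions, neither of which the documents give. It shrinks when the 0 cm result is read alongside the others, and the power advantage of the change test disappears at correlations of 0.5 or below. The primary outcome is not affected. Confidence is medium, because the more favourable reading of the sentence cannot be excluded.

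**What to change.** Replace the independent t-test sentence in the Statistic analysis section with one of these:

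- a between-sex comparison of within-subject change (3 cm minus neutral, and 7 cm minus neutral); or
- a sex-by-position interaction in a repeated-measures or mixed model.

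If the two change tests are used without an overall interaction test, state how the pair is handled, since together they reject in about 9% when there is no difference. Name the neutral reference: first recording, second recording or their mean. Report the male-female difference in change with a 95% confidence interval, and keep the comparisons of values at 0, 3 and 7 cm descriptive.

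The cost is a short rewording of the statistics section. All the measurements are already planned, and no further subjects are needed.

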From this model, relevant clinical parameters can be determined, such as: pelvic obliquity, trunk inclination and kyphosis and lordosis angles (Huysmans et al. 2005; Schulte et al 2008; Betsch et al. 2010).

The reliability coefficients of the rasterstereographic assessment method for the study of the sagittal plane were reported as excellent ($ICC > 0.95$) for both intra-examiner (Schroeder et al. 2015) and inter-examiner (Mohokum et al. 2010). Another systematic review (Mohokum et al. 2015) concluded that rasterstereography can be considered valid for both screening and monitoring.

A recent study (Schroeder and Hollander 2018) used rasterstereography (spinometry) to evaluate the immediate effect in a group of young (less than 24 years old) and middle aged (24 to 56 years old) women who are habitual wearers of high-heeled shoes, after wearing their shoes without heels and with an average heel of 8.7 cm. The results are indicative of a reduction in pelvic tilt and not of lordosis when using the shoe with the heel.

Objective of the study

The aim of this study is, given the remarkable heterogeneity of the data in the literature, to investigate whether artificial heel lift affects spinal posture and pelvic position in the sagittal plane in a group of healthy men and women. A better understanding of the immediate reaction of the spinal column in search of equilibrium during heel lifting could increase the knowledge useful for understanding low back pain associated with the use of shoes with heels and help preventing and/or treating it.

What is meant to prove

The aim of this study is to investigate whether artificial heel lift immediately influences spinal posture and pelvic position in the sagittal plane in a group of healthy male and female subjects not used to wear high-heeled shoes. The recent study by Schroeder and Hollander (2018) used a sample of female subjects with habitual heels; moreover, compared to the previous work, this research also includes the investigation at the level of dorsal kyphosis.

What is added to current knowledge

Given the extreme variability of the data reported in the literature, a better understanding of the adjustments of the immediate reaction of the spine and pelvis to heel elevation. These data could increase knowledge of the pathogenesis of low back pain related to heel height and help prevent or treat it.

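### The heel-height analysis has no primary parameter, no stated order of ANOVA and t-tests and no multiplicity rule, so its false-positive rate is uncontrolled and depends on choices the plan leaves open

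*Combined protocol and SAP*

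**What the plan says.** The Primary outcome paragraph describes a domain, not a variable: the response of the "pelvis, lumbar and dorsal spine in search of balance during the passive elevation of 3 cm and 7 cm of the heels". Under Investigated parameters, six measurements follow with no ranking: pelvic tilt angle, lordotic angle, kyphotic angle, lumbar arrow, cervical arrow and trunk inclination. The first three are grouped in the caption of fig. 1: "Scheme of the spinometric parameters to be recorded: pelvic inclination, lordotic angle, kyphotic angle". They correspond to pelvis, lumbar spine and dorsal spine.

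The Statistic analysis section plans "One-way ANOVA and paired t-test for data for comparison between neutral position, heels raised by 3 cm and 7 cm", and the same bullet ends by applying this to both males and females. The next bullet calculates Cohen's d only for neutral against each rise. Male-female comparisons have their own bullet and serve the secondary outcome. The closing rule for all tests is "Statistical significance will be accepted for p values <0.05".

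The section does not mention a primary contrast, an order in which ANOVA and t-tests are read, a post-hoc procedure or an adjustment. It does not call the analysis exploratory, and it does not say that the one-way ANOVA is repeated-measures, although every subject is measured in every position.

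**The concern.** Several angles, two or three contrasts and two sexes are each tested at 0.05, and nothing states which result answers the primary question. Some nominally significant heel effect then has a substantial chance of appearing even if heel lift does nothing. A reader of the report could not tell a planned finding from the most favourable of many.

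This matters here because the dispute in the literature is about which angle moves. For the closest earlier study the Introduction says: "The results are indicative of a reduction in pelvic tilt and not of lordosis when using the shoe with the heel". Unadjusted testing across angles gives least protection on exactly that question.

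**Working it through.** **The plan's own figure.** There is none to reproduce. The only error-rate figure is the per-test 0.05. The sample size of 100 follows the precedent of a study of 36 women, with no power calculation.

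**Inputs from the documents.** Three angles (fig. 1), three positions (neutral, 3 cm, 7 cm), two sexes of 50 subjects each, 0.05 per test.

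**Assumptions.** Two-sided tests; normal data; correlation between parameters from 0 to 0.9. The documents give no correlations.

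**Count.**
- All pairs of positions: 3 angles x 3 pairs x 2 sexes = 18.
- Rises against neutral only, as in the Cohen's d bullet: 3 x 2 x 2 = 12.

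**Why the independence formula is not used.** 1 - 0.95^18 = 60.3% would apply to 18 independent tests. The contrasts share positions, so the rate was simulated (10,000 to 20,000 replicates; separate runs agree to within about one percentage point).

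**Chance of at least one false heel effect if heel lift changes nothing, three angles, by sex:**

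| Tests | Correlation between angles | t-tests read regardless of ANOVA | Repeated-measures ANOVA required first |
|---|---|---|---|
| 18 | 0 to 0.9 | 55% to 36% | 27% to 16% |
| 12 | 0 to 0.9 | 44% to 28% | 22% to 14% |
| 18 | shared tangents | 48% | 23% |
| 12 | shared tangents | 38% | 20% |

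The shared-tangent rows use the definitions under Investigated parameters. Pelvic tilt and lordosis both use the lumbosacral tangent; lordosis and kyphosis both use the thoracolumbar tangent. These rows assume that the three tangents change independently with equal variance.

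**Arithmetic check at zero correlation.** Simulated rates for one angle in both sexes are 23.4% (all pairs) and 17.6% (against neutral), or 9.8% and 8.1% with the ANOVA required first. For three independent angles:
- 1 - (1 - 0.234)^3 = 55%
- 1 - (1 - 0.176)^3 = 44%
- 1 - (1 - 0.098)^3 = 27%
- 1 - (1 - 0.081)^3 = 22%

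A repeated-measures ANOVA holds error near 5% within one angle and one sex. Six such cells remain: 1 - 0.95^6 = 26.5%.

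**Sexes pooled (n=100), all pairs.** 32% to 20% regardless of ANOVA; 14% to 8% with a repeated-measures ANOVA required first.

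**If the ANOVA is an ordinary between-groups one.** It ignores the pairing. Required first, with 18 tests and independent angles, it leaves 8.6%, 1.8% and 0.0% false effects at within-subject correlation 0.3, 0.5 and 0.9. The price is sensitivity. For a true effect of d=0.5 at 7 cm and half that at 3 cm (n=50), it is significant in 57%, 21%, 4% and 0% of trials at within-subject correlation 0.5, 0.7, 0.8 and 0.9. A repeated-measures ANOVA is significant in about 88%.

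**The case against.** - **The number of tests is a reading.** This stands. A reader might infer that the plan prescribes 18 t-tests read without regard to the ANOVA. The text lists ANOVA and t-tests together and does not settle their order, and the Cohen's d bullet supports 12. Both counts are therefore shown, with and without the ANOVA as a precondition.
- **A false effect is more likely than not.** A reader might infer this from the top of the range. Only zero correlation with 18 tests and no ANOVA requirement exceeds 50%, and zero correlation fits poorly with angles that share tangents. The documents do not support that statement.
- **The three-angle family is itself a choice.** This also stands. The lumbar arrow and the dorsal arrow named in the fig. 2 caption describe regions in the primary outcome. All six parameters over all pairs would give 6 x 3 x 2 = 36 tests, but nothing says that all six are primary, so that is an upper bound.
- **Heels surely change something, so a complete null is unrealistic.** This is fair in part. If pelvic tilt truly changes, fewer null tests remain. In the shared-tangent case with all pairs, the other two angles still give 38% by sex, or 17% with a repeated-measures ANOVA first. This is illustrative only, because lordosis shares a tangent with pelvic tilt.
- **The three regions are separate questions in an investigative study that already reports means, SDs and Cohen's d.** This is a reasonable position and is why labelling the analysis exploratory is a full remedy. The plan does not take that position, however: it keeps a rule for accepting significance.
- **An ordinary ANOVA does not always miss effects.** Correct for large ones. At within-subject correlation 0.8 it is significant in 58% of trials at d=0.8 and 93% at d=1.0, though at 0.9 only in 5% and 32%.

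**Conclusion.** The concern holds. The omissions are plain in the text, and they affect how every primary result is read. For the three angles tested by sex, the chance of at least one false heel effect is about 55% to 36% (18 tests) or 44% to 28% (12 tests) if the t-tests are read regardless of the ANOVA. With a repeated-measures ANOVA first it is about 27% to 16% or 22% to 14%. That requirement alone therefore does not control error across angles and sexes. An ordinary ANOVA first nearly removes false positives at high within-subject correlation, but it misses moderate true effects.

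Confidence is high in the omission and lower in any single rate. The rates assume normal data, no heel effect at all and correlations that the documents do not give. This should be corrected before analysis.

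**What to change.** State that the ANOVA is repeated-measures, and choose one course before analysis.

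**(a) No confirmatory claim intended.** Label the heel-height analysis exploratory. Report every contrast with its mean difference, 95% CI and Cohen's d, and do not use p<0.05 to declare an effect. This costs no power but gives up any claim of significance.

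**(b) Confirmatory claim intended.** Name the primary parameters (for example pelvic tilt, lordotic angle and kyphotic angle) and the contrasts 3 cm and 7 cm against neutral. Apply Holm at 5% across that family and treat everything else as secondary or exploratory. The sponsor then chooses how to handle sex. Power is for d=0.5/0.4/0.3, with d on the SD of the differences (noncentral t):

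| Choice | Tests | First Holm threshold | Power at that step | Power unadjusted |
|---|---|---|---|---|
| Sexes pooled, n=100 | 6 | 0.05/6 = 0.0083 | 99%/90%/62% | 99.9%/98%/84% |
| Sexes separate, n=50 each | 12 | 0.05/12 = 0.0042 | 70%/44%/20% | 93%/79%/55% |

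Pooling keeps more power because it uses 100 subjects, but it displaces the by-sex comparison now in the plan and can hide opposite responses in men and women. Simulated error for the six pooled tests under Holm is 4.9% to 2.8%. Neither course needs new data.
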